7.6.3 Vital Signs, Physical Findings, and Other Observations Related to Safety

7.6.3.1 Vital Signs

Vital sign measurements will be summarized by treatment group and overall. Descriptive statistics will be presented for results and change from baseline at each time point where vital signs were scheduled to be collected.

A shift from baseline to the worst post-baseline blood pressure category (normal to stage 2 hypertension) summary will be presented by treatment group and overall according to each of the American College of Cardiology (ACC) and American Heart Association (AHA) 2017 guidelines as outlined in the Table 18.

Blood Pressure Category	Systolic Blood Pressure		Diastolic Blood
			Pressure
Normal	<120 mmHg		<80 mmHg
	C	and	C C
Elevated	120 - 129 mmHg		<80 mmHg
	C C	and	C C
Stage 1 Hypertension	130 - 139 mmHg		80 - 89 mmHg
		or	
Stage 2 Hypertension	≥140 mmHg		≥90 mmHg
		or	C C

Table 18 Vital Signs ACC/AHA Blood Pressure Categories

Abbreviations: ACC = American College of Cardiology; AHA = American Heart Association

Additionally, temperature will be summarized by treatment group and overall for each visit according to CTCAE grading criteria guidelines as outlined in Table 19.

Table 19CTCAE Grading Criteria for Temperature

CTCAE Grade	Criteria
Grade 0	<38.0 degrees C (<100.4 degrees F)
Grade 1	38.0 – 39.0 degrees C (100.4 - 102.2 degrees F)
Grade 2	>39.0 – 40.0 degrees C (102.3 - 104.0 degrees F)
Grade 3	>40.0 degrees C (>104.0 degrees F) for \leq 24 hrs
Grade 4	>40.0 degrees C (>104.0 degrees F) for >24 hrs

Abbreviations: CTCAE = Common Terminology Criteria for Adverse Events

All vital signs data including scheduled and unscheduled time points will be presented in the participant data listing.

7.6.3.2 12-Lead Electrocardiogram

Twelve-lead ECG continuous parameters (heart rate, PR interval, QT interval, QRS duration, QTc interval corrected for heart rate using Fridericia formula [QTcF] interval) will be summarized by treatment group and overall. Descriptive statistics will be presented for observed values and changes from baseline at each visit where parameters were scheduled to be collected.

ECG recordings will be classified by the investigator as "normal," "abnormal, not clinically significant," or "abnormal, clinically significant." A 3-by-3 contingency table will be presented to summarize the shift from the baseline category to the worst post-baseline value. Summary results will include the count and percentage of participants within each shift category and treatment group.

Prolonged QTcF intervals will be summarized as QTcF measurements (msec) that are $<450, \ge 450$ to 480, >480 to 500, and >500 msec at each visit where ECG is routinely

collected per the clinical study protocol. Change from baseline categories will also be summarized for measurements that represent a change 0 to $<30, \ge 30$ to 60, or >60 msec relative to the baseline value. Summary results will include the percentage of participants within each category and treatment group.

All ECG data including scheduled and unscheduled time points will be listed. Abnormalities occurring at any point in the study post-baseline will also be included in the ECG listing.

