1.3 Schedule of Activities

	Pre- screening (a) Day -45 to C1D1	Screening (a) Day -30 to C1D1		•				End of Treatment (EoT) (c)	Safety Follow- up (d) 30d post EoT (±3d)	Disease Follow- up (e) q3mo post EoT (±14d)	Survival Follow- up (f) q3mo post EoT (±14d)		
Study Day			D1 (g)	D2-7 (±2d)	D8 (±1d)	D22 (±1d)	D1 (±3d)	D2-7 (±2d)	D15 (±2d) (h)				
Pre-screening Informed Consent	X												
Main Informed Consent		X											
Eligibility Review (i)		X	X (i)										
Eligibility Approval Form (i)		X	X (i)										
Randomization (j)			X										
Medical History (k)		X	X										
Demographics		X											
ECOG Status		X	X				X			X	X		
Height		X											
Weight		X	X		X	X	X			X	X		
Vital Signs (l)		X	X	X (1)	X	X	X	X (1)	X	X	X		
Physical Examination (m) (n)		X	X		X (n)	X (n)	X (n)			X	X	X (n)	
Hematology (o), (p), (q)		X (p)	X		X	X	X (q)			X	X	X	

	Pre- screening (a) Day -45 to C1D1	Screening (a) Day -30 to C1D1			cle 1 Days		Cycles 2+ 28 Days Each (b)			End of Treatment (EoT) (c)	Safety Follow- up (d) 30d post EoT (±3d)	Disease Follow- up (e) q3mo post EoT (±14d)	Survival Follow- up (f) q3mo post EoT (±14d)
Study Day			D1 (g)	D2-7 (±2d)	D8 (±1d)	D22 (±1d)	D1 (±3d)	D2-7 (±2d)	D15 (±2d) (h)				
Serum Chemistries (o)		X	X		X	X	X			X	X		
Coagulation (o)		X	X				X			X	X		
Triglycerides, Total Cholesterol (o)		X	X				X			X	X		
Hepatitis Panel (r)		X											
Urinalysis (o)		X	X				X			X	X		
Pregnancy Test (s)		X	X				X			X	X		
Triplicate ECG (t)		X			X	X			X				
AE Monitoring (u)			X	X	X	X	X	X	X	X	X		
Prior/Concomitant Medication Review (v)		X	X	X	X	X	X	X	X	X	X		
RBC and Platelet Transfusions Recorded (w)		X	X	X	X	X	X	X	X	X	X	X	
Dosing Compliance/Diary Review					X	X	X		X	X			
HRQOL (EORTC QLQ-C30, EQ-5D-5L)		X	X				X			X	X	X	
Subsequent Anticancer Therapies (x)											X	X	X

CONFIDENTIAL

	Prescreening (a) Day -45 to C1D1	Screening (a) Day -30 to C1D1							End of Treatment (EoT) (c)	Safety Follow- up (d) 30d post EoT (±3d)	Disease Follow- up (e) q3mo post EoT (±14d)	Survival Follow- up (f) q3mo post EoT (±14d)	
Study Day			D1 (g)	D2-7 (±2d)	D8 (±1d)	D22 (±1d)	D1 (±3d)	D2-7 (±2d)	D15 (±2d) (h)				
Response Assessment (q), (y)							X (q), (y)			X (y)		X (y)	
Bone Marrow Aspirate		X (z)					X (aa)			X (aa)		X (bb)	
Transformation into AML							X			X		X	X
Overall Survival													X
Tamibarotene or Placebo (cc)					Dosii	ng D8-2	28 of ea	ich Cyc	le (cc)				
Azacitidine (dd)			X	X (dd)			X	X (dd)					

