- (e) Patients who have not progressed/relapsed will enter the Disease Follow-up period. Visits should occur every 3 months for response assessment until disease progression/relapse, death, or the occurrence of the expected number of OS events to support the final OS analysis, whichever occurs first. Disease Follow-up Visit window is ±14 days.
- (f) Patients who progress/relapse will be followed to document the start of subsequent anticancer therapy, the date of disease progression/relapse, the date of transformation to AML, and OS status by telephone (or another appropriate method) until the expected number of OS events to support the final OS analysis is observed. Survival Follow-up Visit contact window is ±14 days.
- (g) C1D1 assessments must be performed prior to study drug administration.
- (h) Cycles 2 through 4 only.
- (i) Eligibility review and approval by Sponsor or designee (via Eligibility Approval Form) must be completed prior to randomization.
- (j) Patients can be randomized earlier than C1D1, but within 72 hours of the first dose of study drug, to accommodate operational needs.
- (k) For all randomized patients, any untoward medical occurrences that happen before the first dose of the study drug should be captured as a part of medical history.
- (l) If administration of the 6th and 7th doses of azacitidine of the cycle is delayed to Days 8 and 9 (see footnote (dd)), the vital sign evaluation will shift from Days 6 and 7 to Days 8 and 9 to parallel azacitidine administration. C1D8 vital sign evaluation is required for all patients.
- (m) Definitions for the "full" and "abbreviated" physical examination are provided in Section 8.2.3; both must include an assessment for the presence of extramedullary AML.
- (n) Abbreviated physical examination will be performed at C1D8, C1D22, D1 of Cycles 2+, and at each Disease Follow-up Visit (see Section 8.2.3).
- (o) Laboratory assessments will be performed locally.
- (p) Screening hematology parameter evaluation must be performed prior to or at least 7 days following any blood product transfusion.
- (q) Additional unscheduled hematology evaluations may be performed up to 2 weeks after the bone marrow aspiration, for those patients in marrow CR without full peripheral blood count recovery at the time of the bone marrow aspirate, to assess whether they meet IWG criteria for CR.
- (r) See Section 10.2 for details.

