4 STUDY DESIGN

4.1 Overall Design

This is a Phase 3, multi-center, randomized, double-blind, placebo-controlled study comparing the activity of tamibarotene plus azacitidine to placebo plus azacitidine as first line of therapy in

RARA-positive patients with newly diagnosed HR-MDS. Enrollment in countries in North America and Europe and in Israel is planned.

At the Pre-screening Visit, blood samples will be collected and sent to the Almac Diagnostics Laboratory for assessment of RARA biomarker to determine study eligibility. Pre-screening assessments for the RARA biomarker will be performed within 45 days of Cycle 1 Day 1 and screening assessments for all other eligibility criteria will be performed within 30 days of Cycle 1 Day 1.

Patients will be randomized 2:1 to receive either tamibarotene plus azacitidine or placebo plus azacitidine. Randomization will be stratified by the IPSS-R risk group (Intermediate, High, and Very High Risk) and by geographical region (North America, Western Europe, and Israel versus Eastern Europe); block randomization with a block size of 6 will be used.

Response will be assessed by the investigator per the modified IWG MDS criteria (Cheson 2006). Bone marrow aspirates will be collected to measure response on Day 1 of Cycles 2 and 4, followed by every third cycle (7, 10, 13, etc.), with bone marrow aspirates collected at other times as clinically determined based upon clinical findings or changes in peripheral blood counts. Following the response assessment on Day 1 of Cycle 7, those in CR may have the frequency of bone marrow aspirates for response assessment reduced to every 6 cycles.

Patients will undergo response and safety evaluations throughout their study participation as detailed in the Schedule of Activities (SoA; Section 1.3). Patients may continue to receive study drug until experiencing an unacceptable toxicity, disease progression (including transformation into AML), relapse, decision to pursue post-remission therapy (such as HSCT) or an alternative anticancer therapy, patient withdraws consent, or the investigator determines it is in the best interest of the patient to discontinue study drug.

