The number and percentage of patients with AEs or SAEs will be summarized. Laboratory values and changes in values from baseline will be summarized descriptively by visit, and shift tables will be provided showing change in National Cancer Institute (NCI) CTCAE (version 5) grade from baseline to worst grade postbaseline.

Laboratory Tests

Changes from baseline will be analyzed for each scheduled post-baseline visit for chemistry and hematology parameters. Where applicable, chemistry and hematology laboratory determinations will be categorized according to NCI CTCAE (Version 5) grades, and shift from baseline NCI CTCAE grades to worst post-baseline grades will be assessed.

Vital Signs

A shift from baseline to the worst post-baseline blood pressure category (normal to stage 2 hypertension) summary will be presented by treatment group and total according to each of the American College of Cardiology and American Heart Association 2017 guidelines.

Changes from baseline in systolic and diastolic blood pressure results will also be presented as box plots by visit and for each treatment group.

ECG

A shift from baseline category to the worst post-baseline category (Normal, Abnormal NCS, Abnormal CS) summary will be presented by treatment group and total. Prolonged QTcF intervals (>450 msec, >480 msec, and >500 msec) will be summarized by each visit. Change from baseline categories will also be summarized for measurements that represent a change >30 msec or >60 msec relative to the baseline value.

Change from baseline in QTcF interval results will also be presented as box plots by visit and for each treatment group.

All AE data, vital sign data and ECG data will be listed.

Additional details on the analyses will be provided in the SAP.

Table 4: Estimands (Secondary)

			Estimand Category		
Secondary Objectives	Treatment	Population	Variable/Endpoint	Intercurrent Event; Strategy	Population Level Summary

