7.1.2 Summarization by Visit

Scheduled analysis visits are visits at scheduled timepoints as specified in the protocol. Data summarized by study visit will be based on the nominal, scheduled visit label as reported on the eCRF. For safety analysis, in the case of multiple observations at a specific visit, the latest observation will be used. If more than 1 observation is made on the same day, an average value if continuous or the worst value if categorical will be included in the analysis.

Data collected at unscheduled visits will not be included in the by-visit summaries but will be considered when endpoint derivations potentially include multiple visits (e.g., determination of baseline value, determination of worst post-baseline value, etc.). All data will be included in participant listings.

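### QTcF outliers on unscheduled or repeated ECGs can be absent from every QTcF category table, because the bands are by scheduled visit and no worst post-baseline QTcF table is planned

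*SAP*

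**What the plan says.** **How QTcF is tabulated.** SAP 7.6.3.2 (12-Lead Electrocardiogram) gives four absolute bands: below 450, 450 to 480, and then ">480 to 500, and >500 msec at each visit where ECG is routinely" collected under the protocol. Protocol 9.4.4 (Safety Analyses, ECG) is also by visit: "Prolonged QTcF intervals (>450 msec, >480 msec, and >500 msec) will be summarized by each visit". SAP 7.6.3.2 adds change-from-baseline bands (0 to <30, 30 to 60, >60 msec). That sentence names no visits and does not say that the largest change per participant is taken.

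**When ECGs are scheduled.** The Schedule of Activities (Protocol 1.3) marks triplicate ECGs at Screening, Cycle 1 Day 8, Cycle 1 Day 22 and the Day 15 column for later cycles. Footnote (h) limits that column: "Cycles 2 through 4 only". No ECG is marked at End of Treatment or Safety Follow-up. Treatment itself has no fixed end: "Patients may continue to receive study drug until experiencing an unacceptable toxicity" or another listed stopping reason (Protocol 4.1).

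**What enters a by-visit table.** SAP 7.1.2 states: "Data collected at unscheduled visits will not be included in the by-visit summaries". The same sentence admits such data to derivations that span visits, such as a worst post-baseline value. For safety data it also says that "in the case of multiple observations at a specific visit, the latest observation will be used", except that same-day continuous values are averaged. SAP 7.1.3.8 averages the three reads of a triplicate.

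**What else exists for ECGs.** SAP 7.6.3.2 has a 3-by-3 shift table from baseline to worst post-baseline, but for the investigator's normal/abnormal classification. All ECGs, scheduled or not, are listed.

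**The concern.** An ECG taken outside the schedule is often prompted by something, such as a symptom or an earlier long QTcF. Those ECGs are more likely than routine ones to show an outlier, and they are the ones left out of the QTcF bands. Within a visit, averaging or replacement can also pull a peak into a lower band.

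QTcF matters enough here to be an exclusion criterion (Protocol 5.2, criterion 18). The SAP already uses worst post-baseline values for laboratory grades (7.6.2), liver tests (7.6.2.1), blood pressure (7.6.3.1) and ECOG status (7.6.3.4). QTcF in msec has no counterpart. At stake is a report whose QTcF tables show nobody above 500 msec while such a value sits in a listing.

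**Working it through.** The documents give no figure to reproduce. The check is calendar arithmetic plus a reading of the rules together.

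**1. Schedule.** Take undelayed 28-day cycles with Cycle 1 Day 1 as Day 1, so day = (cycle − 1) × 28 + cycle day.
- C1D8 = 8 and C1D22 = 22
- C2D15 = 28 + 15 = 43
- C3D15 = 56 + 15 = 71
- C4D15 = 84 + 15 = 99, the last scheduled ECG
- C7D1 = 6 × 28 + 1 = 169, the primary-endpoint visit

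The gap is 169 − 99 = 70 days.

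**2. Dosing after the last scheduled ECG.** Tamibarotene/placebo is planned on Days 8 to 28, 21 days per cycle.
- Before C7D1: 6 × 21 = 126 days
- Up to and including C4D15: 3 × 21 + 8 = 71 days
- After it: 126 − 71 = 55 days, and 55/126 = 44%

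Dosing can continue past C7D1. Any ECG after the C4D15 visit is necessarily unscheduled.

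**3. Applying SAP 7.1.2.** The values are assumed, for illustration only: one recording of 510 msec and one of 470 msec.

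| Situation | Value used | Band shown |
|---|---|---|
| 510 at a scheduled visit; 470 repeat recorded as unscheduled | 510 | >500 |
| Both under one scheduled label, repeat on a later day | 470 | 450 to 480 |
| Both under one scheduled label, same day | (510 + 470)/2 = 490 | >480 to 500 |
| 510 on an unscheduled ECG | none | absent |
| Participant's worst value, all ECGs | 510 | >500 |

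The first row keeps the outlier; the next three lose it.

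**4. Other ECG outputs.** By-visit descriptive statistics include a maximum, and the protocol plans by-visit box plots of QTcF change. Both are by-visit summaries, so the same exclusion applies. The worst post-baseline shift table may draw on unscheduled ECGs under SAP 7.1.2, but it carries a classification and no msec value. SAP 7.1.2 would let a worst post-baseline QTcF use unscheduled data, but no such QTcF output is defined. The change categories could be read either way.

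**The case against.** The strongest reply is that the SAP follows the protocol, which also asks for QTcF bands by visit, and that nothing is lost: every ECG is listed, so a maximum-value table could be made later. Both statements are true. They mean this is no departure from plan and the data are safe. They do not supply a planned table that counts participants above 480 or 500 msec.

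Several stronger readings are tempting and the documents do not support them.

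- *Outliers vanish from every summary table.* They need not. An unscheduled ECG can enter the worst post-baseline shift table, and an ECG finding judged clinically significant is an adverse event (Protocol 10.3.1) and so reaches the TEAE tables. Both routes depend on the investigator, and neither counts participants by QTcF band.
- *Only the latest repeat is ever kept.* Same-day values are averaged. A later-day repeat displaces the first value only if it is entered under the same scheduled visit label. If it is recorded as unscheduled it is dropped and the first value stands. The documents do not say which is usual.
- *The change categories are by visit only.* Their sentence states no visit restriction. That is an ambiguity to settle.
- *Time without a scheduled ECG measures the data lost.* For 12 cycles one would get (336 − 99)/336 = 71%, but no 12-cycle duration is stated. Like the 44% above, it describes the ECG schedule. A new table cannot fill time in which no ECG was taken.

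Two further differences are minor. The SAP puts exactly 450 msec (and a change of exactly 30) in the higher band, unlike the protocol, and it has no category for decreases. Neither affects detection of clear prolongation.

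**Conclusion.** The point holds for the QTcF category tables. The absolute bands use scheduled visits only, and those end at C4D15 (Day 99, 70 days before C7D1, assuming no cycle delays). Unscheduled ECGs are excluded, repeats under one visit label are averaged or replaced, and no participant-level worst QTcF table is specified. A value above 480 or 500 msec can therefore be seen only in listings, or through investigator judgement in the shift or TEAE tables.

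The number of participants affected cannot be estimated: the documents give no count of unscheduled ECGs and no QTcF results. No efficacy endpoint, hypothesis test or alpha is touched. The change should be made before database lock, because a planned count is more credible than one added after outliers have been seen. This is a comment on tabulation, not on when ECGs should be taken.

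**What to change.** Add to SAP 7.6.3.2 a participant-level table, by treatment group, on Safety Analysis Set 1:

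- maximum post-baseline QTcF: >450, >480 and >500 msec;
- maximum increase from baseline: >30 and >60 msec;
- source: every post-baseline ECG (scheduled, unscheduled and repeat) through last dose + 30 days, matching the TEAE window in SAP 7.6.1;
- unit: the mean of the triplicate for each recording, with no averaging across separate recordings;
- cut points: the protocol's strict inequalities.

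State in the same paragraph whether the existing change categories are by visit. Keep the by-visit tables as descriptive. They remain useful because a maximum tends to rise with the number of ECGs taken, while the by-visit tables compare the arms on a common schedule.

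The cost is a short SAP addition and one extra table. The data are already collected and listed, and no trial procedure changes.

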7.6.3.3 Physical Examination

Any abnormal clinically significant finding identified during the physical examination will be recorded as medical history or AE depending on when it started or worsened. A by-participant listing of the physical examination dates will be provided.

7.6.3.4 ECOG Performance Status

ECOG performance scores will be summarized by treatment group and total. The number and percentage of participants will be presented by ECOG performance score (ranging from 0 to 5) at each time point where ECOG performance scoring was scheduled to be collected. The change from baseline by visit will be summarized by descriptive statistics. Additionally, a 6-by-6 contingency table will be presented to summarize the shift from the baseline category to the worst post-baseline score. Summary results will include the count and percentage of participants within each shift category and treatment group. Byparticipant ECOG performance status results will be provided in a listing.

7.7 Determination of Sample Size

There is expected to be a high correlation between CR achieved by Cycle 7 Day 1 and CR achieved at any time (Silverman 2006; VIDAZA UPSI), and therefore, same effect size and other design assumptions are justified in the sample size determination.

CCI participants will provide **CCI** power to detect the difference in CR rates between the tamibarotene plus azacitidine treatment group and the placebo plus azacitidine treatment group, with assumed CR rates of **CCI** versus **CCI** in the 2 treatment groups, respectively, a 2:1 randomization, and 1-sided alpha of **CCI**.

A total of **CO** death events will provide **CO** power to detect the difference in OS between tamibarotene plus azacitidine treatment group and the placebo plus azacitidine treatment group, with assumed median survival of **CO** months versus **CO** months (hazard ratio = **CO**) in the 2 treatment groups, respectively, a 2:1 randomization, and 1-sided alpha of **CO**.

A total of approximately **CCI** participants (**CCI** in the tamibarotene plus azacitidine treatment group and **CCI** in the placebo plus azacitidine treatment group) are expected to

be randomized in this study to obtain the ^{CCI} death events and final analysis time at approximately 70 months.

8 CHANGES IN THE CONDUCT OF THE STUDY OR PLANNED ANALYSES

The planned analyses outlined in this SAP include changes from the protocol as outlined below:

8.1 Summary of Changes in Version 4.0

8.1.1 Duration of CR and Duration of Overall Response

In Sections 6.4.1.3, 7.4.5.3, and 7.4.5.4, "failure" has been removed as one of the possible events for DOCR and duration of overall response calculation because it is expected that worsening of response after CR/PR/mCR/HI will be captured by disease progression or relapse of disease. This change has been applied throughout the document.

